# **13.2** Sample Size, Accrual Rate and Study Duration

As stated above, 11 patients will be enrolled in the first stage of the study, with a planned second stage of 25 patients if at least 7 patients in the first-stage are progression-free at nine months. The null will be rejected and the study deemed positive if at least 23 total patients are progression-free at 9 months.

We expect to accrue approximately 10-15 patients/year, therefore assuming the study advances to the second stage and that there may be a brief pause in enrollment between the first and second stage (to allow for patients to reach the 9 month endpoint), will complete accrual for the study within 3 years. Final data for the primary endpoint will be mature within 4 years.

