## **1. OBJECTIVES**

## 1.1 Study Design

This is a single arm, open-label phase II study evaluating the safety and efficacy of the combination of the third-generation EGFR inhibitor EGF816 with the first-generation EGFR inhibitor gefitinib in the treatment of TKI-naïve *EGFR*-mutant non-small cell lung cancer. The study will have a Simon two-stage design with eleven patients enrolled in the first stage and a plan to enroll a total of 36 patients (25 patients in the second stage) if at least seven patients remain progression-free at nine months in the first stage. The first six patients enrolled in the study will constitute a safety run-in evaluating the safety of the combination of EGF816 at the recommended phase II dose of 150mg QD and gefitinib at a standard dose of 250mg QD. If unexpected toxicities are observed among the first six patients, expansion cohorts will be added to explore different doses and/or schedules of the combination.

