# **13. STATISTICAL CONSIDERATIONS**

# 13.1 Study Design/Endpoints

This is a phase II study designed to evaluate the efficacy of the combination of EGF816 and gefitinib in the first-line treatment of EGFR-mutant non-small cell lung cancer. The primary endpoint is proportion of patients free from progression at 9 months. The study is designed as a Simon two-stage study. The null hypothesis is that EGF816 does not add any benefit to gefitinib monotherapy, with the assumption that the median PFS for gefitinib monotherapy is 9 mo, in other words 50% of patients will be free from progression at 9 months. The study is designed to have 80% power at the 0.05 significance level to show that the combination regimen of gefitinib plus EGF816 increases the proportion of progression-free patients at 9 months to 73% using a

one-sided binomial test. The total study size is 36 patients. 11 patients will be enrolled in the first stage of the study, with a planned second stage of 25 patients if at least 7 patients in the first-stage are progression-free at nine month. The rejection criteria for the null would be having 23 patients who are progression-free by 9 months. Based on our prior experience with first-line treatment of pateints with EGFR mutant NSCLC, we do not expect any patients to be lost to follow-up or unevaluable prior to the 9 month timepoint.

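### Section 13.2 sets no rule for enrolment while stage 1 matures; deciding stage 1 at the 5th failure or the 7th nine-month success closes most of the gap at no cost in error rates

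*Combined protocol and SAP*

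**What the plan says.** Section 1.1 opens the second stage "if at least seven patients remain progression-free at nine months in the first stage". Section 13.1 repeats the condition: "if at least 7 patients in the first-stage are progression-free at nine month". Section 13.2 says that "11 patients will be enrolled in the first stage of the study" and restates the same condition for the other 25.

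The only statement about enrolment during the wait is in the accrual paragraph of 13.2. It assumes that "there may be a brief pause in enrollment between the first and second stage" so that patients can reach the nine-month endpoint. The same paragraph expects 10 to 15 patients a year, accrual complete within 3 years and mature primary data within 4.

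Section 13.5 marks interim monitoring as not applicable. Section 12.2 gives the monitoring committee toxicity and accrual to review. Neither says who makes the stage-1 decision or when.

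**The concern.** A two-stage design earns its complexity by treating few patients when the regimen is no better than the null. That works only if the stage-1 result is acted on before many second-stage patients have entered. Here the endpoint takes nine months, which at the planned accrual is long enough to enrol a large part of stage 2. A pause that may happen and is expected to be brief does not tell the site whether to keep registering.

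The stage-1 result is also often settled well before the 11th patient reaches nine months. The plan makes no use of this: the only timing it mentions is waiting for patients to reach nine months. At stake are patient exposure and the early-stopping saving, not the validity of the final test.

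**Working it through.** **Inputs.** From 13.1: null rate 0.50 ("50% of patients will be free from progression at 9 months"), alternative 0.73, a "one-sided binomial test" with "80% power at the 0.05 significance level". From 13.1 and 13.2: 11 then 25 patients, continue on at least 7 of 11, reject on at least 23 of 36, accrual 10 to 15 a year. From 5.2 and Table 10-1: CT every 8 weeks in the first year.

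**The plan's design.** The rejection probability is the sum over x = 7 to 11 of P(X1 = x) × P(X2 ≥ 23 − x), with X1 ~ Bin(11, p) and X2 ~ Bin(25, p).
- p = 0.50: 0.048
- p = 0.73: 0.811

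The stated design reproduces. The probability of stopping, P(X1 ≤ 6), is 0.726 at 0.50 and 0.149 at 0.73.

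**Does a full wait fit the stated timeline?** Accrual takes 36/rate × 12 months, plus 9 for a full wait after the 11th entry. Maturity is 9 months later.

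| Rate per year | Accrual, no pause | Accrual, full wait | Data mature, full wait |
|---|---|---|---|
| 15 | 28.8 mo | 37.8 mo | 46.8 mo |
| 12 | 36.0 mo | 45.0 mo | 54.0 mo |
| 10 | 43.2 mo | 52.2 mo | 61.2 mo |

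Three years cannot hold a full wait at any stated rate, and at 10/year it fails with no pause at all. Four years holds with a full wait only at about 14.4/year or faster (36 / (30/12) = 14.4).

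**Ceiling on early entry.** With no pause and stage 1 read when the 11th patient reaches nine months, entries are rate × 9/12: 7.5 at 10/year and 11.25 at 15/year, or 30% to 45% of the 25. A 3-month pause gives 5.0 to 7.5, 6 months gives 2.5 to 3.8, and 9 months gives 0.

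**Expected enrolment under the null.**
- No early entry: 11 + 25 × 0.274 = 17.9
- Ceiling, 10/year: 17.9 + 0.726 × 7.5 = 23.3
- Ceiling, 15/year: 17.9 + 0.726 × 11.25 = 26.0

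The saving against a fixed 36 is 18.1, so the ceiling gives back 5.4 to 8.2 of it.

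**Deciding as soon as the result is fixed.** After 5 failures at most 11 − 5 = 6 successes remain possible, so 7 cannot be reached. After 7 nine-month successes the condition is already met. Each trial gets the same stage-1 answer as with full follow-up, so alpha stays at 0.048 and power at 0.81.

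Timing was simulated (100,000 trials per setting, exponential PFS, Poisson accrual) against a reading when the 11th patient reaches nine months:

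| Null stop, range over 10 to 15/year | Progression known at once | Known at next 8-weekly scan, or at nine months if sooner |
|---|---|---|
| Months earlier | 6.5 to 7.6 | 5.6 to 6.8 |
| Stage-2 patients entered first, no hold | 1.8 to 3.5 | 2.3 to 4.5 |
| Known before the 11th entry | 16% to 31% | 9% to 23% |

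Using the scan-based column, null expected enrolment without a hold is 17.9 + 0.726 × 2.3 = 19.6 to 17.9 + 0.726 × 4.5 = 21.2. At p = 0.73, the decision to continue comes 1.6 to 2.4 months earlier.

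**The case against.** The strongest reply is that the pause wording belongs to an accrual forecast, while the conditional wording in 1.1, 13.1 and 13.2 can be read strictly as barring second-stage entry until the condition is met. This stands. A reader might infer that the protocol makes the hold optional, or permits enrolment through the decision. The documents do not say so; they are silent, and the gap is a missing rule.

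A reader might also take 8 to 11 patients as the expected early exposure. It is a ceiling that needs both no pause and a reading only at the 11th patient's nine months. The plan asserts neither, and nothing in it prevents an open-label team from acting on the 5th failure.

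Nor is there an error-rate problem. While 7 of 11 is enforced on the first 11, early entry leaves alpha alone. Alpha for 23 of 36 reaches 0.066 only if the stage-1 rule is ignored, which the plan does not propose. If the regimen works, early entry costs little: at p = 0.73, expected enrolment rises from 32.3 to at most 33.4 to 33.9.

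Finally, a mandatory hold is not free. It falls on the 85% of trials that pass stage 1 at p = 0.73, and early reading recovers only 1.6 to 2.4 of the nine months. Trading exposure against time is the sponsor's choice. None of this removes the case for writing down when stage 1 is decided.

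**Conclusion.** The point holds as a missing operational rule in 13.2 and an accrual forecast that does not fit a full wait. The consequence is limited to exposure: at most 7.5 to 11.3 stage-2 patients before the decision, and null expected enrolment of at most 23.3 to 26.0 against 17.9. Any partial pause gives less. Type I error and power are sound as planned.

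The clear improvement is the early decision rule, which changes no error rate and still makes a null stop known about 5.6 to 6.8 months earlier with 8-weekly scans. The documents do not establish that a hold must be mandatory.

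The timing figures assume exponential PFS, Poisson accrual at 10 to 15 a year, no loss before nine months (as 13.1 expects), and nine-month status known at nine months. The stopping probabilities, alpha and power are exact binomial results and do not depend on the PFS shape or accrual pattern.

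**What to change.** Add to 13.2: *Stage 1 is decided on the first 11 patients at whichever comes first: the 5th failure (progression or death before nine months), when enrolment closes; or the 7th patient progression-free at nine months, when stage 2 opens.* Name who tracks stage-1 status and declares the decision. The cost is this text and a running status log; sample size, thresholds and error rates stay as they are.

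Separately, state whether stage-2 registration waits for the decision. If it does not, the exposure to accept is about 2.3 to 4.5 patients ahead of a null stop. If it does, revise both time statements. With a full wait, accrual is 37.8 to 52.2 months. With the early rule at p = 0.73 it averages about 28.8 + 9 − 1.6 = 36.2 months at 15/year and 43.2 + 9 − 2.4 = 49.8 at 10/year, with data mature about 9 months later (45.2 and 58.8). The 3-year figure needs correcting at the low end of the accrual range in any case, since 10/year already takes 43.2 months without a hold.

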# **13.3** Patient Disposition

A detailed description of patient disposition will be provided. It will include:

- A definition of patient enrollment
- A summary of data regarding patient discontinuation of study treatment
- A summary of data regarding patient inclusion and exclusion in efficacy and safety analyses

# **13.4** Patient Characteristics

Patient characteristics will include a summary of the following:

- Patient demographics
- Baseline disease characteristics
- Baseline tumor molecular characteristics
- Significant medical history and co-morbidities
- Concomitant therapies
- Other characteristics as appropriate

## 13.5 Interim Monitoring Plan- N/A

## **13.6** Analysis of Primary Endpoints

The primary end-point is proportion of patients free from objective disease progression or death at 9 months. Progression will be defined by RECIST 1.1

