# 5. TREATMENT PLAN

## 5.1 Treatment Regimen

All patients will receive combination therapy with EGF816 and gefitinib in an open-label fashion. A treatment cycle will be defined as 28 days. After completing 1 year of study treatment, visits will occur every 6 weeks.

The first six patients enrolled in the study will constitute a safety run-in; if severe unexpected toxicities are observed during cycle 1 among these six patients, further expansion cohorts at lower dose levels will be explored. Severe unexpected toxicities will be defined as any grade 3 or higher adverse event assessed to be treatment-related by the treating physician occurring in > 1/6 patients during the safety run-in. Rash will be excluded as grade 3 rash during the 1st cycle has occured with each drug individually and is typically responsive to dose hold. If >1 patient has a grade 3 or higher treatment-related adverse event during cycle 1 of treatment, we will de-escalate treatment to gefitinib 250 mg QD and EGF816 100 mg QD.

EGF816 will be supplied by Novartis to the investigational drug pharmacy at all participating sites. Gefitinib will be supplied directly to the patient through prescription as a commercial product. As stated in the eligibility criteria, only patients with insurance approval to obtain gefitinib or who agree to self-pay for gefitinib will be able to participate in this study. Upon signing of the study ICF and confirmation of eligibility, participants will be prescribed a 30-day (one 28-day cycle; with two additional pills in case of lost, dropped pills) supply of gefitinib. C1D1 will begin only once the supply of gefitinib is in the patient's possession.

All patients will receive gefitinib 250 mg orally once daily and EGF816 100 mg orally once daily without interruption, unless an interruption is required to manage treatment-related toxicity (as outlined in Tables 6-1 and 6-2). Patients will be monitored at the start of each 28-day treatment cycle. Treatment will be administered on an outpatient basis. The participant will be requested to maintain a medication diary of each dose of medication. The medication diary will be returned to clinic staff at the end of each cycle.

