## 6. DOSING DELAYS/DOSE MODIFICATIONS

Dose delays and modifications will be made as indicated in the following table(s). The descriptions and grading scales found in the revised NCI Common Terminology Criteria for Adverse Events (CTCAE) version 4.0 will be utilized for dose delays and dose modifications. A copy of the CTCAE version 4.0 can be downloaded from the CTEP website http://ctep.cancer.gov/protocolDevelopment/electronic\_applications/ctc.htm.

Dose delays and modifications will be made as indicated in the following table(s). The descriptions and grading scales found in the revised NCI Common Terminology Criteria for Adverse Events (CTCAE) version 4.0 will be utilized for dose delays and dose modifications. A copy of the CTCAE version 4.0 can be downloaded from the CTEP website http://ctep.cancer.gov/protocolDevelopment/electronic applications/ctc.htm.

EGF816 and gefitinib are both EGFR tyrosine kinase inhibitors and have both overlapping and distinct toxicities. Guidelines for the management of potentially drug-related toxicities, including dose interruptions and dose reductions of each drug, are provided in section 6.1.

When possible, toxicities should be managed with appropriate medical treatment (including antiemetics, anti-diarrheals, etc.) Other contributing factors, including concomitant medications which may be contributing to the toxicity, should be identified and discontinued or dose reduced if appropriate. The following sections provide guidelines for dose modification and dose interruption (i.e., interruption and re-initiation criteria for EGF816 and gefitinib treatment). All dose modifications should be based on the worst preceding toxicity (CTCAE version 4.0). If, due to study drug related toxicity, a patient requires a dose interruption of >28 days from the intended day of the next scheduled dose, then the patient must be discontinued from the study treatment. Each patient is allowed no more than two dose reductions of each study drug. In addition, a patient must discontinue treatment with EGF816 and gefitinib if, after treatment is resumed at a lower dose, the toxicity recurs with the same or worse severity.

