# 12.2 Data Safety Monitoring

The DF/HCC Data and Safety Monitoring Committee (DSMC) will review and monitor toxicity and accrual data from this study. The committee is composed of clinical specialists with experience in oncology and who have no direct relationship with the study. Information that raises any questions about participant safety will be addressed with the Overall PI and study team.

The DSMC will review each protocol up to four times a year or more often if required to review toxicity and accrual data. Information to be provided to the committee may include: up-to-date participant accrual; current dose level information; DLT information; all grade 2 or higher unexpected adverse events that have been reported; summary of all deaths occurring with 30 days of intervention for Phase I or II protocols; for gene therapy protocols, summary of all deaths while being treated and during active follow-up; any response information; audit results, and a summary provided by the study team. Other information (e.g. scans, laboratory values) will be provided upon request.

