# 13.7 Analysis of Secondary Endpoints

Response rate will be assessed as per RECIST, see Section 9.1. Results will be reported with 95% confidence intervals. All patients will be evaluable for response rate. Progression-Free Survival (PFS) will be defined as the duration of time from start of treatment to time of objective disease progression or death. Overall survival (OS) will be defined as the duration of time from start of treatment until death. Analysis will be performed using the Kaplan-Meier method. All patients will be evaluable for survival endpoints.

A summary of the adverse events, grading according to CTCAE and their attributed relatedness to treatment will be provided as a measure of patient safety and tolerability. All patients will be included in the safety analyses.

The first six patients in the study will constitute a safety cohort as outlined in section 5.1. If >1 patient has a grade 3 or higher treatment-related adverse event during cycle 1 of treatment, the dose will be de-escalated as outlined. Six additional patients will be treated at the lower dose to establish safety prior to proceeding to open enrolment of the remainder of the trial. The probability of stopping at the initial dose in order to dose de-escalate and the probability of stopping the trial after the safety run in at the lower dose based on assumptions about the associated underlying toxicity rates are as follows:

True toxicity rate	Probability of reducing the starting dose	Probability of stopping the trial
0.05	0.265	0.033
0.1	0.468	0.114
0.2	0.738	0.345
0.3	0.883	0.580
0.4	0.954	0.767
0.5	0.985	0.890

Biopsies from pre, post and on-treatment will be obtained to facilitate comparative analysis by next-generation sequencing, single-cell RNA sequencing, transcriptional profiling and an evaluation of the emergent resistance mechanisms at the time of progression. Analyses for these outcomes may include the Cox proportional Hazard models for the examination of the relationship between changes in sequencing parameters and time to progression, Sign-Rank test to compare pre and post measurements of gene expression for genes of interest and other correlation tests such as linear regression to examine relationship between relevant outcomes.

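### After the six-patient, cycle-1 run-in, no pre-specified toxicity boundary applies to later patients or to later events, and committee review has no threshold

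*Combined protocol and SAP*

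**What the plan says.** **Run-in.** Section 5.1: "The first six patients enrolled in the study will constitute a safety run-in; if severe unexpected toxicities are observed during cycle 1", lower-dose cohorts follow. Section 13.7 gives the count: "If >1 patient has a grade 3 or higher treatment-related adverse event during cycle 1 of treatment, the dose will be de-escalated as outlined". Section 5.1 carves out one event: "Rash will be excluded as grade 3 rash during the" first cycle has been seen with each drug alone. After a de-escalation, Section 13.7 adds six patients at the lower dose before general enrolment.

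**After the run-in.** Section 13.5 is "Interim Monitoring Plan- N/A". By Sections 13.1 and 13.2, "The total study size is 36 patients", enrolled as 11 and then 25. The second stage opens if at least 7 of the first 11 are progression-free at nine months; toxicity plays no part. The rules in Section 6 act on the individual patient, not on accrual.

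**Committee.** Section 12.2: "The DSMC will review each protocol up to four times a year or more often if required to review toxicity and accrual data". Its list of possible inputs is open-ended. The only adverse-event item is "all grade 2 or higher unexpected adverse events that have been reported". The list also names DLT information, deaths within 30 days and a study-team summary, with other data on request. The protocol does not define a DLT for this trial.

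**Other reporting.** Serious adverse events go to the Overall PI (7.2.1), to Novartis within 24 hours (7.2.3) and, where they qualify, to the FDA (7.3). Adverse events go to the institutional review office (7.2.2).

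**The concern.** This combination's foreseeable harm is more of what each drug already does. Section 6 says so: "EGF816 and gefitinib are both EGFR tyrosine kinase inhibitors and have both overlapping and distinct toxicities". An excess of that kind shows in a running count against a denominator, and seldom in a single report. The plan makes such a count once, on six patients over 28 days. Treatment then continues until progression, and safety and tolerability is a secondary objective (Section 1.3). If the run-in passes by chance, nothing obliges anyone to tally again, whatever the later patients experience.

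**Working it through.** **Inputs.** Run-in of 6, trigger at 2 or more events (5.1, 13.7). Total 36, as 11 + 25 (13.1). If the starting dose is kept, 36 − 6 = 30 patients follow: 5 in stage 1 and 25 in stage 2. True event rates p are assumptions, taken from the range in the 13.7 table plus 1/6.

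**1. The plan's own table.** Let X be binomial with n = 6.

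- At p = 0.2: P(X = 0) = 0.8^6 = 0.262 and P(X = 1) = 6 × 0.2 × 0.8^5 = 0.393.
- P(X ≥ 1) = 1 − 0.262 = 0.738. This is the table's probability of reducing the starting dose.
- P(X ≥ 2) = 1 − 0.262 − 0.393 = 0.345. This is the table's probability of stopping the trial.

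All six rows follow this pattern to within 0.001. The dose-reduction column therefore matches a rule of at least 1 of 6, while the text says more than 1. The stopping column is the chance of 2 or more in one cohort of six, not of two cohorts failing in turn (0.345² = 0.119 at p = 0.2 if the rate were the same in both).

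**2. Passing the run-in under the written rule.** P(pass) = (1 − p)^6 + 6p(1 − p)^5. Expected later cycle-1 events = 30p.

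| True rate p | P(pass) | Expected events in 30 |
|---|---|---|
| 0.1 | 0.886 | 3 |
| 0.2 | 0.655 | 6 |
| 0.3 | 0.420 | 9 |
| 0.4 | 0.233 | 12 |
| 0.5 | 0.109 | 15 |

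If the rule behind the dose-reduction column was intended, P(pass) = (1 − p)^6, which is 0.262, 0.118 and 0.047 at 0.2, 0.3 and 0.4. Later patients still have no rule.

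**3. What a cumulative boundary would add.** For illustration, refer to the committee at 4 of 11, 6 of 18, 7 of 24 or 9 of 30, counting the run-in event over all patients at the current dose. The calculation is an exact recursion. Start from 0 or 1 event in six patients, weighted by the two terms in step 2. Add binomial counts for the next 5, 7, 6 and 6 patients. At each look remove the probability at or above the boundary, then divide the total removed by P(pass).

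| True rate p | P(boundary fires, given a passed run-in) |
|---|---|
| 0.1 | 0.007 |
| 1/6 | 0.07 |
| 0.2 | 0.14 |
| 0.3 | 0.50 |
| 0.4 | 0.84 |
| 0.5 | 0.97 |

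This covers the toxicity rules only, with independent patients, one constant cycle-1 rate, no de-escalation and no efficacy stop.

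**The case against.** The strongest reply is that later patients are not unwatched, and that is so. Three stronger readings are tempting, and the documents do not support them.

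- *The committee sees only unexpected events.* Section 12.2 gives it toxicity data generally, through a non-exhaustive list that includes 30-day deaths and anything it requests, and it may meet more often if required. The Grade 2+ unexpected events are the only adverse-event item named, not the only data available.
- *The committee is the only safeguard.* Serious-event reporting under Sections 7.2 and 7.3 covers every patient, including after day 28. It works case by case, however, and carries no cumulative count rule.
- *Excess known toxicity is excluded because it is expected.* Section 7.1 also calls an event unexpected when its frequency or intensity departs from the Investigator's Brochure. Nor is a reference rate wholly absent: Section 2.2.2 prints single-agent EGF816 figures, such as 29.7% with related Grade 3/4 events and 15.5% with related Grade 3/4 rash. What is missing is a threshold that turns a count into a required review.

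Two objections to a boundary also have force. The documents state no unacceptable rate, so any cut-off offered here is illustrative. And a boundary on the run-in event leaves out rash and everything after cycle 1; those can be put before the committee cumulatively, but without a number attached.

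**Conclusion.** The gap is real and modest in scope. After the run-in there is no pre-specified toxicity boundary for later patients or for any event after cycle 1, and committee review is discretionary, with no threshold and no mandated hold. Under the written rule, rates of 0.3 and 0.4 pass with probability 0.42 and 0.23, leaving about 9 and 12 expected events in the next 30 patients.

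Three limits apply. First, 30 assumes that the starting dose is kept. After a de-escalation it is 24 if both safety cohorts count within the 36, which the documents do not say. Second, 25 of the 30 are treated only if the efficacy gate is passed.

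Third, a reader might take 0.42 as the chance of reaching 36 patients without a pause. It is not: the gate passes with probability 0.274 at 50% progression-free and 0.851 at 73%. If efficacy and toxicity are independent, the chance of reaching 36 at a toxicity rate of 0.3 is 0.42 × 0.274 = 0.12 to 0.42 × 0.851 = 0.36. Section 13.2 also allows for a brief pause between stages, although for the nine-month endpoint. What is absent is a mandated toxicity pause.

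**What to change.** **First reconcile.** Bring the run-in rule and the 13.7 table into agreement. Reconcile Section 1.1, which gives 150 mg of EGF816 for the run-in, with Sections 5.1, 5.3.1 and 6.1, which give 100 mg as the daily dose or level 0, while Section 5.1 also gives 100 mg as the de-escalated dose. Which is intended is for the sponsor to state.

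**Section 13.5.** Replace the N/A entry with a cumulative boundary on the run-in event, counted over all patients treated at the current dose. If it is reached, new accrual is held until the existing committee has reviewed the data. The sponsor sets the unacceptable rate and prints the operating characteristics beside the 13.7 table. The cut-offs above only show the form.

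**Section 12.2.** At each such review give the committee the cumulative any-cycle count of Grade 3+ treatment-related events, expected or not and including rash, with toxicity discontinuations and treatment-related deaths. Keep the Grade 2+ unexpected item. Define DLT information as the run-in event, or delete it.

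No dose or patient-level rule changes.

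**Cost.** Protocol wording and a running tally of data already collected, sent to a committee that already exists. With the illustrative cut-offs, the chance of an unneeded hold after a passed run-in is about 7% at a true rate of 1/6 and 14% at 0.2.
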